# 8.3 Participant population

The patients will be recruited from scheduled Dermatology out-patient clinics including routine general Dermatology clinics and staff members working at UHCW NHS Trust (study arm 1: dry skin conditions) OR two week wait (2WW) urgent Dermatology clinics for suspected skin cancer, and joint clinics run between Dermatology and Plastic Surgery (study arm 2: known or suspected skin cancer). Patients will be selected based on clinical diagnosis. Patients will not be randomised.

## 8.4 Procedure(s) to account for missing or spurious data

Data will be collected on the day of recruitment and no further patient data will be collected after this, with the exception of histological results (study arm 2). Histological results are securely stored on the University Hospitals of Coventry and Warwickshire Clinical Results Reporting System (CRRS). As part of a cancer care pathway, these patients are tracked by the Cancer Support Team and Cancer MDT Facilitator to ensure data is not lost.

In the rare event that THz skinometer scan data is lost (e.g. not recorded, deleted in error) then the accompanying patient information will be removed from the SINATRA study.

As part of this feasibility study, a wide range of data is expected, and so spurious data will be included into the study analysis.

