# **STUDY SUMMARY**

Full study title	SkIN hydrAtion evaluation with TeRAhertz scanning
Short study title	SINATRA Study
Study aim	Pilot study to confirm feasibility, test recruitment, trial procedures and refine intervention delivery.
Study design	Single centre, non-randomised, Pilot trial
Study participants	Patients with suspected/confirmed skin cancer and patients with benign dry skin conditions
Study arms	
 
Benign dry skin condition group
 
Skin cancer group (either confirmed basal cell carcinoma and/or suspected malignant melanoma)
 

Sample size	150 (ratio of 2:1 so 100 in the skin cancer group and 50 in the benign dry skin condition group) Within the skin cancer group we will aim for 50 basal cell carcinoma patients and 50 malignant melanoma patients
Planned study period	24 months
Planned recruitment start date	15/03/2022
Planned recruitment end date	15/03/2023
Planned study end date	30/03/2024
Objectives	
 
To undertake a feasibility study
 
To assess skin hydration and confirmed/suspected skin cancer water content with terahertz imaging.
 

Primary Objective	The primary objective will be to explore the feasibility, test recruitment, trial procedures and refine intervention delivery
Secondary Objective	To explore if Terahertz skinometry can quantify skin hydration and will show an increase in skin water content after application of an emollient in dry skin conditions.  To explore if Terahertz skinometry can quantify skin hydration and many indicate the presence of residual basel.
	hydration and may indicate the presence of residual basal cell carcinoma after primary excision, or the localised inflammation caused by melanoma skin cancer.

Key Words: SKIN; CANCER; TERAHERTZ; IMAGING; DIAGNOSIS; NOVEL

Figure 1: Participant Flow Chart

<sup>1There will typically be 7 quality THz scans in this arm of the study. Areas of interest may be scanned up to a maximum of 3 times at each time point in order to ensure a clear image is received.

<sup>2There will typically be 3 quality THz scans in this arm of the study. Once identified, each area will be scanned up to a maximum of 3 times to ensure a meaningful datasets acquired. If multiple cancerous areas are identified, the one that gives the clearest image will be chosen. This may involve scanning multiple cancerous areas before a decision is made as to which area is most suitable to pursue.

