Study arm 2: The arm with 100 patients with known or suspected skin cancer will have a scan with the THz skinometer in the clinic prior to their planned skin surgery. They will be scanned on the cancerous area, a control area and a reference standard area (the volar forearm) for a minimum of 3 quality scans. In the event that the reference standard and control area are the same, then the participant will only have a minimum of 2 quality scans. The purpose of the reference standard area scan is to act as a calibration point and so we can compare a between subject variable as well as the within subject variable from the cancer/control area. If a participant has multiple potentially cancerous areas on their body, the team will decide which of these areas to scan for the study. If it occurs that the chosen area is too difficult to scan/doesn't produce a clear enough image then a different cancerous area will be selected. There will be a maximum of 3 scans conducted at each of the cancerous area, control area and reference standard area in order to obtain a meaningful dataset. Later the results of the THz scan will be compared to the formal histology results after the primary (melanoma) or residual (BCC) tumour has been removed.

For patients with multiple skin conditions (i.e. multiple dry skin or cancerous locations on the body), we will select the area that is most practical to scan and can make good contact with the scanner.

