## 3. OBJECTIVES AND OUTCOME MEASURES/ENDPOINTS

## 3.1 Primary objective

The primary objective will be to explore the feasibility, test recruitment, trial procedures and refine intervention delivery.

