## 3.3 Primary endpoint/outcome

## Feasibility outcomes measures:

- Number of patients screened, eligible, recruited, withdrawn and retained
- Willingness of participants to participate in the trial

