## 7.3 Trial assessments

After patient recruitment, individuals will have a photo taken of the area of skin to be scanned before being scanned with the THz skinometer. A non-toxic Easi-Mark Surgical Skin Marker will be used to draw around the area to be scanned for image registration (both study arms) and to control the amount of skin product applied in the fixed area (study arm 1 only). This will be performed by a delegated research team member in an appropriate environment as per standard trust policy.

- A. **Study arm 1**: A minimum of 6 (most likely 7) readings of the THz skinometer ("scan") will be conducted after measuring the area of interest (AOI) and area of unaffected skin (control area measurement), at the following time points:
  - 1. Pre-application THz skinometer ("scans") of the AOI and area of unaffected skin, and the reference standard (volar forearm)

- 2. Post-application scan-I: participant will then be requested to apply emollient used regularly by them to the dry skin and control area, following which after 10 minutes another THz skinometer ("scans") will be conducted of the AOI and control area
- 3: Post-application scan-II: Repeat scans of AOI and control area will be conducted 10 minutes following the post-application scan-I

Further scans may be required if a clear image is not received upon the first attempt. At each time point each area will be scanned a maximum of 3 times to ensure a clear image is received.

Following the completion of the scans this will be the end of participation in the trial and the patient will continue the standard treatment pathway.

**Study arm 2**: A minimum of 2 (most likely 3) readings of the THz skinometer ("scan") will be conducted after measuring the AOI, area of unaffected skin (control area measurement) and the reference standard (volar forearm).

As with study arm 1; each area can be scanned up to 3 times to ensure a clear image is received. If a participant has multiple cancerous areas on their body the team will select the area most appropriate/feasible to scan. If they are unable to receive a good image, they will select another area instead.

This will be the end of participation in the trial and the patient will continue the standard treatment pathway. Histological diagnosis will be collected remotely using patient notes/medical records at a later date (typically 2-4 weeks after biopsy) by a delegated research team member.

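### Section 8.4 removes participants whose scans are lost and keeps undefined spurious readings, so procedural losses can drop out of the feasibility counts and invalid values can enter the hydration means

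*Protocol*

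**What the plan says.** Protocol section 8.4 sets two rules.

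- Lost scans: the section calls such loss rare and gives failure to record and accidental deletion as examples. Its rule for that case is: "then the accompanying patient information will be removed from the SINATRA study". The removal is from the study, not only from the hydration analysis.
- Spurious values: "a wide range of data is expected, and so spurious data will be included into the study analysis". The term is not defined.

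The objective in 3.1 is to "explore the feasibility, test recruitment, trial procedures and refine intervention delivery". The first primary outcome in 3.3 is "Number of patients screened, eligible, recruited, withdrawn and retained"; the second is willingness to take part. Neither 3.3 nor the rates described at the start of section 8 count scan success, repeat scans or changes of area.

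Sections 1.4 and 7.3 allow up to three scans of each area (at each time point in arm 1) so that a clear image is obtained. A participant with several lesions can be moved to another one: in 1.4, if the chosen area "doesn't produce a clear enough image then a different cancerous area will be selected"; in 7.3, "If they are unable to receive a good image, they will select another area instead". On which lesion to use, footnote 2 to the flow chart in the Study Summary says "If multiple cancerous areas are identified, the one that gives the clearest image will be chosen", whereas 1.4 and 7.3 choose on ease of access and contact with the scanner.

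Hydration is compared by paired t-tests, one-way ANOVA and independent t-tests. Section 8 ties the case for a larger study to mean differences and their 95% CIs.

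**The concern.** A feasibility study of a new scanner should show how often the procedure yields data that can be used. The rule for lost scans works against this, because the participants in whom the procedure went wrong leave the study, and the recruited and retained counts with it. Taken literally, their baseline and adverse event records from the scan visit go too. A later trial would then be planned on completeness figures from which the losses have been taken out.

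The rule for spurious data works in the other direction. Means and t-tests are sensitive to gross errors, and the wording admits erroneous readings as well as genuine extremes. It also sits awkwardly beside repeat scanning for image quality: poor scans are screened out at acquisition, yet spurious values are promised a place in the analysis.

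The two statements on lesion choice add a smaller uncertainty about which measurement represents a participant with several lesions.

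**Working it through.** **1. The plan's own figure.** Section 8.1 gives 50 per group, standardised difference 0.5, 10% significance and 80% power. The noncentrality is 0.5 × √(50/2) = 2.5. With 98 degrees of freedom and a two-sided test the power is 79.9% (normal approximation: Φ(2.5 − 1.645) = 80.4%). The figure reproduces and is not in dispute. Sidedness is not stated; a one-sided 10% test would give 88.8%, so two-sided is what was used.

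**2. The removal rule.** The documents call loss rare and give no rate, so the rates here are assumptions, applied to all 150 participants.

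| Assumed loss | Participants | Rate if counted (exact 95% CI) | Rate after removal |
|---|---|---|---|
| 2% | 3 | 2.0% (0.4% to 5.7%) | 0 of 147 |
| 5% | 8 | 5.3% (2.3% to 10.2%) | 0 of 142 |
| 10% | 15 | 10.0% (5.7% to 16.0%) | 0 of 135 |

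The effect on the hydration tests is minor: 45 per group instead of 50, if not replaced, gives power of 76.1%. What is lost is the failure rate itself, which the study is large enough to estimate.

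**3. Which primary rates are touched.** In section 8, willingness comes from steps 1 and 2, eligibility from step 3 and recruitment from step 4 (consent). All precede the scan, so these rates can be computed unchanged. The counts exposed are recruited and retained, if removed participants are no longer counted.

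**4. The spurious-data rule.** Assume one reading in each group of 50 is replaced by an error of k SD with random sign. The SD is multiplied by about √((49 + k²)/50), and the standardised difference is 0.5 divided by that.

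| k | SD multiplier | Standardised difference | Power, formula | Power, simulated (40,000 runs) |
|---|---|---|---|---|
| 3 | √(58/50) = 1.08 | 0.46 | 74.5% | 74.3% |
| 5 | √(74/50) = 1.22 | 0.41 | 65.4% | 65.0% |
| 8 | √(113/50) = 1.50 | 0.33 | 50.3% | 49.9% |

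Leaving the invalid reading out instead (49 per group) gives 79.2%.

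**5. Lesion choice.** The Study Summary footnote selects after seeing the image; 1.4 and 7.3 select on practicality, with a swap if imaging fails. If clarity were the same thing as the hydration contrast, taking the better of two lesions correlated at 0.5 (assumed) would add √((1 − 0.5)/π) = 0.40 SD in those participants. If 20% of participants had two lesions (assumed), the group mean would move by 0.2 × 0.40 = 0.08 SD.

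**The case against.** The best defence is that section 8.4 deals with a narrow event. Its examples are mostly record-keeping losses, it calls them rare, and it does not name a scan that was obtained but poor. A reader might infer that all scan failure vanishes from the study, or that retention is biased upward by construction. The text does not support that: screening data are kept for everyone invited (7.1.1), the section 8 rates predate the scan, and 3.3 gives no formula for retention. Nothing forbids logging attempts. This limits the reach of the point, but the instruction to remove the participant from the study remains and conflicts with counting those recruited and retained.

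On spurious data, the stated reason (a wide expected range) suggests that the authors meant not to trim extreme values, which is sensible in a pilot. Repeat scanning should also stop many artefacts reaching the analysis. Both arguments are fair. The undefined word still covers erroneous readings, and the sentence commits to including them. The analyses affected are secondary and exploratory.

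On lesion choice, a reader might infer a 0.4 SD exaggeration of the lesion-control difference. No section equates clarity with contrast, 1.4 links an unclear image to difficult access, and only participants with several areas are concerned.

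Thresholds for a technical quality check may properly sit in a SAP, and their absence here is not a fault.

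**Conclusion.** The point holds for two stated rules and one inconsistency. Followed literally, the removal rule takes procedural losses out of two primary counts; that conflict needs no assumed number. At assumed losses of 2% to 10%, the reported loss would be 0%. The spurious-data rule admits invalid readings to comparisons of means. One per group of 50 would lower the power from 80% to about 75%, 65% or 50% at 3, 5 or 8 SD; these sizes are illustrations, since the documents give neither an error rate nor an error size. It would be too strong to say that the stated power is mostly lost: even two 8 SD errors per group leave about 37%, and milder errors cost far less. Any bias from choosing the clearest image is unquantified, and 0.4 SD is a worst-case bound for participants with several areas only.

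**What to change.** 1. In 8.4, replace the removal rule: every consented participant stays in all feasibility counts; lost or unusable scans are reported per group with the reason; the participant is omitted only from those hydration analyses that need the missing scan.
2. In 3.3, add the proportion of participants with an analysable scan set on the first-chosen area, together with repeat scans and area substitutions, per group.
3. In 8.4, replace the spurious-data sentence: genuine extreme values are kept; technically invalid scans, identified without knowledge of histology or the hydration result, are excluded from the main hydration analysis; an analysis of all data is reported as a sensitivity analysis. The thresholds can be left to the SAP.
4. Reconcile the Study Summary footnote with 1.4 and 7.3: choose the index area on accessibility and contact before imaging, and record any later swap.

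The cost is protocol wording and a scan-log field, with no extra visits or scans. The downside is that reported completeness may look less favourable. The change should be made before records are removed, because removed participants and unlogged attempts may not be recoverable.

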#### 9 DATA MANAGEMENT

#### 9.1 Data collection tools and source document identification

Digital scan data will be collected and stored on a dedicated password protected PC or hard drive. Each data set will be assigned a unique Identification Code. Patient identifiable data will be stored in the Study Site File (Patient Hospital Number) on a participant identification log.

Subsequent biopsy results (study arm 2) that will be collected as part of the routine NHS care pathway will be identified from the University Hospitals of Coventry and Warwickshire Clinical Results Reporting System (CRRS) by the Principle Investigator who is a clinical member of NHS staff. The result will be anonymised and linked to the unique patient ID to then be linked to the THZ skinometer data.

#### 9.2 Access to Data

The SINATRA Study data sharing plan is outlined below:

- 1) Patient recruitment and progress will be updated continuously throughout the timeline of the project via an Institutional website (University Hospitals Coventry and Warwickshire NHS Trust) led by the UHCW Research and Development department and the UHCW Innovation Hub, of which the lead applicant is Clinical Innovation Lead.
- 2) The Patient and Public Involvement (PPI) group will be updated on patient recruitment in addition to institutional websites, via the Clinical Research Nursing team.
- 3) Pseudonymised patient data will not be shared outside of the primary study group. This will be used to link the skinometer measurements with clinical histopathological results within the remit of the SINATRA study.
- 4) Anonymised patient data (e.g. number of patients, age range, sex) will be shared during the final data analysis within the timeline of the project and subsequent public release of data. Anonymised patient data may be shared with future researchers (academic or commercial) at the discretion of the chief investigator if the participant has consented to this.
- 5) A data-sharing agreement will be used to impose appropriate limitations on the secondary use of the data.
- 6) The UHCW R&D team, UHCW Innovation team and the University of Warwick (Warwick Ventures) will be informed of all developments where there might be a potential for commercial interest, and in particular prior to any data sharing. It may be necessary to delay data sharing and modify any data sharing plan to ensure that patient benefit can be maximised.

7) The final dataset will consist of anonymised patient metadata (e.g. number of patients, age range, sex) and skinometry measurements.

## 9.3 Archiving

Following the resolution of queries and confirmation of study close-out by the Chief Investigator, all essential documentation will be transferred to a third-party archiving service, which provides suitable fire and water-resistant facilities. Study files will be archived for a period of 25 years. Access to the study documentation will be restricted to named individuals within the study team with express permission from the Chief Investigator.

## 10. Safety Monitoring

The THZ scanner is a non-invasive diagnostic tool which emits million times lower energy than an x-ray and thus doesn't have enough energy to cause ionisation. The power levels used in the THz systems in this study are also very low such that there are no lasting effects. In particular, our *in vivo* THz imaging systems have a peak power less than 40mW and average power intensity less than 4  $\mu$ W/cm². Studies by Hough et al [2] have shown that even using peak power 50,000 times higher and an average intensity 30 times higher does not cause any change in gene expression. Therefore, power levels used in our THz in vivo imaging systems are safe and have no known side effects or risks

Considering, participants will only vary from their usual care at the point of baseline data acquisition. The trial team will therefore not report any of the following events happening 30 minutes after the final THz scan.

# 10.1 Definitions (from ISO/FDIS 14155)

## 10.1.1 Adverse Device Effect (ADE)

Adverse event related to the use of an investigational medical device.

NOTE 1- This includes any adverse event resulting from insufficiencies or inadequacies in the instructions for use, the deployment, the installation, the operation, or any malfunction of the investigational medical device.

NOTE 2- This includes any event that is a result of a use error or intentional misuse.

## 10.1.2 Adverse Event (AE)

Any untoward medical occurrence, unintended disease or injury or any untoward clinical signs (including an abnormal laboratory finding) in subjects, users or other persons whether or not related to the investigational medical device.

NOTE 1: This includes events related to the investigational device

NOTE 2: This includes events related to the procedures involved (any procedure in the protocol).

NOTE 3: For users or other persons this is restricted to events related to the investigational medical device.

## 10.1.3 Device deficiency

Inadequacy of a medical device related to its identity, quality, durability, reliability, safety or performance, such as malfunction, misuse or use error and inadequate labelling.

## 10.1.4 Investigational medical device

Medical device being assessed for safety or performance in a clinical investigation.

## 10.1.5 Serious Adverse Device Effect (SADE)

Adverse Device Effect that has resulted in any of the consequences characteristic of a serious adverse event.

## 10.1.6 Serious Adverse Event (SAE)

Adverse event that:

- a) led to a death,
- b) led to a serious deterioration in health that either:
- 1) resulted in a life-threatening illness or injury, or
- 2) resulted in a permanent impairment of a body structure or a body function, or
- 3) required in-patient hospitalisation or prolongation of existing hospitalisation, or
- 4) resulted in medical or surgical intervention to prevent life threatening illness or injury or permanent impairment to a body structure or a body function.
- c) led to foetal distress, foetal death or a congenital abnormality or birth defect.

NOTE 1: This includes device deficiencies that might have led to a serious adverse event if: a) suitable action had not been taken or b) intervention had not been made or c) if circumstances had been less fortunate. These are handled under the SAE reporting system.

NOTE 2: A planned hospitalisation for pre-existing condition, or a procedure required by the Clinical Investigation Plan, without a serious deterioration in health, is not considered to be a serious adverse event.

## 10.1.7 Unanticipated Serious Adverse Device Effect (USADE)

Serious adverse device effect which by its nature, incidence, severity or outcome has not been identified in the current version of the risk analysis report.

NOTE: Anticipated: an effect which by its nature, incidence, severity or outcome has been previously identified in the risk analysis report.

## 10.2 Reporting procedures

Participants will have the opportunity to report any events during the baseline data acquisition, but will also direct contact with the trial team by telephone and email to report any events at a later stage.

